### Assessment of Causality

- The investigator is obligated to assess the relationship between study treatment and each occurrence of each AE/SAE.
- A "reasonable possibility" of a relationship conveys that there are facts, evidence, and/or arguments to suggest a causal relationship, rather than a relationship cannot be ruled out.
- The investigator will use clinical judgment to determine the relationship.
- Alternative causes, such as underlying disease(s), concomitant therapy, and other risk factors, as well as the temporal relationship of the event to study treatment administration will be considered and investigated.
- The investigator will also consult the Investigator's Brochure (IB) and/or Product Information, for marketed products, in his/her assessment.
- For each AE/SAE, the investigator **must** document in the medical notes that he/she has reviewed the AE/SAE and has provided an assessment of causality.
- There may be situations in which an SAE has occurred and the investigator has minimal information to include in the initial report to GSK. However, **it is very important that the investigator always make an assessment of causality for every event before the initial transmission of the SAE data to GSK.**
- The investigator may change his/her opinion of causality in light of follow-up information and send an SAE follow-up report with the updated causality assessment.
- The causality assessment is one of the criteria used when determining regulatory reporting requirements.

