**Period 2:**

- There will be a washout of at least 14 days between the administration of nemiralisib in Period 1 and the administration of nemiralisib in Period 2.
- Participants will be admitted to the clinical research unit on Day -1 and will remain in-house until collection of the final PK sample on Day 11.
- From Day 1 to 10 inclusive, participants will receive a single dose of 200 mg itraconazole in the morning.
- On Day 5, participants will receive a single dose of 100 mcg nemiralisib one hour after the dose of 200 mg itraconazole.

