**Table 3 Period 2**

Procedure	Treatment Period Days												Notes
	-1	1	2	3	4	5	6	7	8	9	10	11	
Admission	X												
Discharge												X	
Alcohol breath test & drug screen	X												Includes urine cotinine test
Brief physical examination	X											X	
Laboratory assessments (hematology, clinical chemistry and urinalysis)	X										X		Pre-dose at all timepoints. Day -1 results to be reviewed before dosing on Day 1.
Clinical chemistry only			X		X		X		X				Pre-dose at all timepoints. Day 4 results to be reviewed before itraconazole dosing on Day 5.
12-lead ECG		X	X		X		X		X		X		Single measurement. Pre-dose and 3h post-dose (itraconazole) on Day 1. Pre-dose at all other timepoints, Day 4 results to be reviewed before itraconazole dosing on Day 5.
Vital signs		X	X		X		X		X		X		Single measurement. Pre-dose at all timepoints
Study treatment (itraconazole)		X	X	X	X	X	X	X	X	X			Approx. 1 h post standard meal.
FEV 1					X								Triuplicate
Inhaler (Ellipta) training					X								Training conducted by reviewing the Patient Information Leaflet with the participant. Additional training may be conducted at the discretion of the investigator.
Study treatment (nemiralisib)						X							1 h post itraconazole administration.
PK (nemiralisib)						X	X	X	X	X	X	X	pre-dose, and 5 min, 30 min, 2 h, 6 h, 12 h, 24 h, 48 h, 72 h, 96 h, 120 h and 144 h post-dose (nemiralisib)

Procedure	Treatment Period Days											Notes
	-1	1	2	3	4	5	6	7	8	9	10	
PK (itraconazole + hydroxy-itraconazole)		X				X	X					Pre-dose, 30 min, 1 h, 1.5 h, 2 h, 3 h, 4 h, 6 h, 8 h, 12 h post-dose (itraconazole) on Day 1  Pre-dose, 30 min, 1 h, 1.5 h, 2 h, 3 h, 4 h, 6 h, 8 h, 12 h and 24 h hours post-dose (itraconazole) on Day 5
AE review		←=====→										
SAE review	X	←=====→										
Concomitant medication review	X	←=====→										

- The timing and number of planned study assessments, including safety and pharmacokinetic assessments may be altered during the course of the study based on newly available data (e.g., to obtain data closer to the time of peak plasma concentrations) to ensure appropriate monitoring.

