### 5.1. Overall Design

This is a Phase I, single centre, open label, one sequence cross-over study to be conducted in healthy males and females of non-child bearing potential. The study will evaluate the PK, safety and tolerability of nemralisib when administered alone and when

administered concomitantly with repeat doses of itraconazole, a known strong inhibitor of CYP3A4, to simulate a steady-state exposure of itraconazole.

The pharmacokinetics of itraconazole and hydroxy-itraconazole (its hydroxy-metabolite) will be assessed to provide precise estimates of its pharmacokinetics to validate and support any interaction observed with nemiralisib as well as future usage via *in silico* modelling for nemiralisib and other drugs.

Each participant will participate in the study for approximately 7 weeks. They will complete a screening visit, 2 treatment periods (nemiralisib alone followed by nemiralisib co-administered with itraconazole), and a follow up visit (see Figure 1).

**Figure 1** Overall study schematic

Screening:

Participants must be screened within 21 days before the first dose (Day 1), and must meet all eligibility criteria.

Period 1:

- Participants will be admitted to the clinical research unit on Day -1 and will remain in-house until collection of the final PK sample on Day 6.
- On Day 1, participants will receive a single dose of 100 mcg nemiralisib.

Period 2:

- There will be a washout of at least 14 days between the administration of nemralisib in Period 1 and the administration of nemralisib in Period 2.
- Participants will be admitted to the clinical research unit on Day -1 and will remain in-house until collection of the final PK sample on Day 11.
- From Day 1 to 10 inclusive, participants will receive a single dose of 200 mg itraconazole in the morning.
- On Day 5, participants will receive a single dose of 100 mcg nemralisib one hour after the dose of 200 mg itraconazole.
- Participants will receive the administration of nemralisib on Day 5 and itraconazole doses on Day 5 to Day 10 only if there are no findings that are considered clinically significant by the Investigator (in consultation with the medical monitor if needed) during review of Day 4 clinical chemistry and ECG.
- Itraconazole will be administered at approximately the same time every day and approximately 1 h after a standard breakfast.
- Nemralisib will be administered at approximately the same time in Period 1 and in Period 2.

Follow-up:

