## 7. TREATMENTS

Study treatment is defined as any investigational treatment(s), marketed product(s), placebo, or medical device(s) intended to be administered to a study participant according to the study protocol.

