### **8.1.4. Other study stopping criteria**

A participant will be discontinued from the study if they experience a serious adverse event and/or unacceptable adverse events, as determined by the investigator and/or medical monitor. Every effort should be made to complete safety follow-up procedures after a participant is discontinued from study drug.

The study will be halted for an internal safety review if there is a SAE or 2 severe AEs, considered to be at least possibly related to the study treatment (nemiralisib or itraconazole).

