11.8.7. Safety Tables

Safety: Tables					
No.	Population	IDSL / Example Shell	Title	Programming Notes	Deliverable [Priority]
Adverse Events (AEs)					
3.1.	Safety	AE1CP /	Summary of All Adverse Events by System Organ Class and Preferred Term	ICH E3	SAC
3.2.	Safety	AE1CP	Summary of All Drug-Related Adverse Events by System Organ Class and Preferred Term	ICH E3	SAC
Laboratory: Chemistry					
3.3.	Safety	LB1	Summary of Chemistry Changes from Baseline	ICH E3 Include baseline values. Add Footnote: 'Nemirisib was administered on Day 1 of Period 1 and Day 5 of Period 2'.	SAC
Laboratory: Hematology					
3.4.	Safety	LB1	Summary of Hematology Changes from Baseline	ICH E3 Include baseline values. Add Footnote: 'Nemirisib was administered on Day 1 of Period 1 and Day 5 of Period 2'.	SAC
Laboratory: Urinalysis					
3.5.	Safety	UR3b	Summary of Urine Dipstick Results	ICH E3 Add Footnote: 'Nemirisib was administered on Day 1 of Period 1 and Day 5 of Period 2'.	SAC

Safety: Tables					
No.	Population	IDSL / Example Shell	Title	Programming Notes	Deliverable [Priority]
Laboratory: Hepatobiliary (Liver)					
3.6.	Safety	LIVER1	Summary of Liver Monitoring/Stopping Event Reporting	IDSL	SAC
3.7.	Safety	LIVER10	Summary of Hepatobiliary Laboratory Abnormalities	IDSL	SAC
ECG					
3.8.	Safety	EG1	Summary of ECG Findings	IDSL Add Footnote: 'Nemiralisib was administered on Day 1 of Period 1 and Day 5 of Period 2'	SAC
3.9.	Safety	EG2	Summary of Change from Baseline in ECG Values by Visit	IDSL Include baseline values. Add Footnote: 'Nemiralisib was administered on Day 1 of Period 1 and Day 5 of Period 2'.	SAC
Vital Signs					
3.10.	Safety	VS1	Summary of Change from Baseline in Vital Signs	ICH E3 Include baseline values. Add Footnote: 'Nemiralisib was administered on Day 1 of Period 1 and Day 5 of Period 2'.	SAC

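### AE relatedness is required only against study treatment, meaning either drug, so the drug-related AE table compares nemiralisib-related events in Period 1 with events related to either drug in Period 2

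*Protocol*

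**What the plan says.** Protocol Appendix 4, under Assessment of Causality, sets the requirement: "The investigator is obligated to assess the relationship between study treatment and each occurrence of each AE/SAE". Protocol section 7 gives the term a wide meaning: "Study treatment is defined as any investigational treatment(s), marketed product(s), placebo, or medical device(s) intended to be administered". Section 7.1 then lists two study treatments, nemiralisib and itraconazole. The study halt rule in section 8.1.4 uses the same either-drug sense, for events "considered to be at least possibly related to the study treatment (nemiralisib or itraconazole").

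Dosing differs by period. Period 1 has one nemiralisib dose and no itraconazole. For Period 2, Protocol section 5.1 says: "From Day 1 to 10 inclusive, participants will receive a single dose of 200 mg itraconazole in the morning". The synopsis adds: "On Day 5, participants will receive a single dose of 100 mcg nemiralisib one hour after the dose of 200 mg itraconazole".

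On the display side, SAP section 11.8.7 plans Table 3.2, "Summary of All Drug-Related Adverse Events by System Organ Class and Preferred Term", with no drug named. SAP section 5.1 provides two display groups: nemiralisib alone, and nemiralisib with itraconazole. There is no itraconazole-alone group. SAP section 11.2.2 opens the Period 2 treatment-emergent window at the first itraconazole dose and closes it 10 days after the nemiralisib dose.

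The secondary safety objective (Protocol section 4) concerns single-dose nemiralisib, given alone and concomitantly with itraconazole.

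**The concern.** A by-treatment table of related events invites the reader to compare its columns and attribute the difference to co-administration. Here the label changes meaning between columns. In Period 1 only nemiralisib can be the related drug. In Period 2 it may be either drug, and itraconazole is given daily while nemiralisib is given once. An excess in Period 2 could then come entirely from itraconazole's known reactions.

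Protocol section 3.3.1 lists 12 common itraconazole reactions, including cough and sore throat. Some lie close to what the plan watches for with nemiralisib: bronchospasm and mucosal irritancy in the same section, and post-inhalation cough as the AE of special interest in SAP section 8.2. The study has one sequence and no itraconazole-alone group, so the investigator's attribution is one of the few ways to describe what nemiralisib contributed. As required, it pools the two drugs. The protocol rationale says the study data will inform eligibility criteria and possibly dose modification in other nemiralisib studies. An unexplained rise in drug-related AEs could be misread in that setting.

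**Working it through.** The plan states no figure for this point, so the check sets the definitions side by side, counts doses and days, and gives one illustration with assumed rates.

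**1. Meaning of 'related' in each column of Table 3.2**

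| | Period 1 | Period 2 |
|---|---|---|
| Nemiralisib doses | 1 (Day 1) | 1 (Day 5) |
| Itraconazole doses | 0 | up to 10 |
| 'Related' can mean | nemiralisib | nemiralisib or itraconazole |

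The text of Protocol section 5.1 gives 10 − 1 + 1 = 10 itraconazole doses. The itraconazole row of the Period 2 Schedule of Activities, as extracted, marks nine days (Days 1 to 9). The two places must be reconciled, but the argument does not depend on which count applies.

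**2. Time covered by each column (SAP section 11.2.2)**

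- Period 1: Day 1 to Day 1 + 10 = Day 11, which is 11 calendar days.
- Period 2: Day 1 to Day 5 + 10 = Day 15, which is 15 calendar days.
- Period 2 before the nemiralisib dose: Days 1 to 4, which is 4 of 15 days (27%).
- Period 2 from the nemiralisib dose: Days 5 to 15, which is 11 days, the same length as Period 1.

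Events with onset on Period 2 Days 1 to 4 have no column other than the combination one.

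**3. What the Period 2 count can support**

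Count participants with at least one related event. Let N be those with an event judged related to nemiralisib, and I those whose related events are all judged related to itraconazole only. The column reports N + I. Hence N cannot exceed the reported count, which is a valid upper limit. In Period 1 the column reports N alone. The contrast between columns therefore includes I, and nothing in the table allows I to be removed.

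**4. Illustration of I (assumed rates)**

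The documents list itraconazole's common reactions without frequencies. Suppose a fraction q of n = 16 participants has itraconazole-only related events and nemiralisib contributes none. The expected addition is nq, and the chance of at least one such participant is 1 − (1 − q)^n.

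| q (assumed) | nq | chance of at least one |
|---|---|---|
| 5% | 16 × 0.05 = 0.8 | 56% |
| 10% | 16 × 0.10 = 1.6 | 82% |
| 20% | 16 × 0.20 = 3.2 | 97% |
| 30% | 16 × 0.30 = 4.8 | over 99% |

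With 20 participants the expected addition runs from 1.0 to 6.0. The assumed rate decides the figure.

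**The case against.** The strongest reply has four parts.

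*The objective is still addressed.* A reader might infer that the plan cannot show nemiralisib's safety with itraconazole. The documents do not support that. The objective concerns nemiralisib taken concomitantly with itraconazole, which is the regimen the Period 2 column describes. The endpoint is adverse events plus laboratory values, vital signs, ECG and spirometry, not drug-related events alone. Table 3.1 covers all AEs whatever their cause, and Tables 3.3 to 3.10 do not use AE attribution as their endpoint. This part stands: the weakness is confined to how Table 3.2 is read.

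*The CRF may already ask per drug.* The AE page is not among the documents and the table shells are available only on request. Appendix 4 also sends the investigator to the Investigator's Brochure and to product information for marketed products, so thinking about each product is expected. A reader might infer that the per-drug field is missing. The documents show only that it is not required. This stands and shapes the fix.

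*Listings help.* With about 20 participants, Listing 13 can be read in full. Its footnote gives the nemiralisib day, and SAP section 11.4.3 derives AE time since first dose. Post-inhalation cough has its own term and Listing 19. This stands in part: onset timing identifies events on Days 1 to 4, but cannot separate the drugs from Day 5, when both have been given.

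*Attribution is opinion.* From Day 5, in an open-label study, assigning a cough to one drug is a judgement. A reaction caused by itraconazole raising nemiralisib exposure belongs to both. Splitting the table does not remove the confounding of a one-sequence design. This also stands, and is why the split can only be supportive.

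**Conclusion.** The point holds as a limitation of one table and of the causality requirement behind it. Relatedness is required only against either drug, and Table 3.2 inherits that. Its Period 1 versus Period 2 contrast mixes nemiralisib's contribution with itraconazole's own reactions, including events from the 4 of 15 window days before the Period 2 nemiralisib dose. The table does describe related AEs under the combined regimen and bounds the nemiralisib-related ones from above.

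The size is not known from the documents. The figure of about 1 to 5 additional participants rests entirely on assumed itraconazole-only rates of 5% to 30% in 16 participants. The conclusion also assumes that the CRF holds no more detail than the protocol requires; if it does, only the display needs to change. The primary pharmacokinetic analysis is unaffected, and the study tests no formal hypothesis. The change is still worth making because per-drug attribution not captured at the time of the event is hard to reconstruct reliably later.

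**What to change.** 1. State in Protocol Appendix 4 that relationship to nemiralisib and relationship to itraconazole are recorded as two separate items for each AE and SAE, with both allowed to be positive. If the CRF already does this, say so.
2. Show SAP Table 3.2 by causal drug: nemiralisib-related for both periods and itraconazole-related for Period 2. Keep the either-drug count alongside, which also serves the halt rule in section 8.1.4 as worded.
3. Show Period 2 AEs in two parts: onset before the nemiralisib dose, and onset on or after it. This rests on dates rather than opinion, and the second part matches the Period 1 window at 11 days.
4. Describe the per-drug split as supportive, and leave the all-AE Table 3.1 in place.

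The cost is at most one CRF item, one additional table and a subdivision of the Period 2 display. The downside is that attribution from Day 5 remains a judgement, so the split should not be read as separating the two drugs' effects.

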### Follow-up of AE and SAE

- The investigator is obligated to perform or arrange for the conduct of supplemental measurements and/or evaluations as medically indicated or as requested by GSK to elucidate the nature and/or causality of the AE or SAE as fully as possible. This may include additional laboratory tests or investigations, histopathological examinations, or consultation with other health care professionals.
- If a participant dies during participation in the study or during a recognized follow-up period, the investigator will provide GSK with a copy of any post-mortem findings including histopathology.
- New or updated information will be recorded in the originally completed CRF.
- The investigator will submit any updated SAE data to GSK within 24 hours of receipt of the information.

## Reporting of SAE to GSK

### SAE Reporting to GSK via Paper CRF

- Facsimile transmission of the SAE paper CRF is the preferred method to transmit this information to the **SAE coordinator**.
- In rare circumstances and in the absence of facsimile equipment, notification by telephone is acceptable with a copy of the SAE data collection tool sent by overnight mail or courier service.
- Initial notification via telephone does not replace the need for the investigator to complete and sign the SAE CRF pages within the designated reporting time frames.
- Contacts for SAE reporting can be found in the SRM.

## 12.5. Appendix 5: Contraceptive Guidance and Collection of Pregnancy Information

### Definitions

#### Woman of Childbearing Potential (WOCBP)

A woman is considered fertile following menarche and until becoming post-menopausal unless permanently sterile (see below)

#### Women in the following categories are not considered WOCBP

1. Premenarchal
2. Premenopausal female with ONE of the following:
  - Documented hysterectomy
  - Documented bilateral salpingectomy
  - Documented bilateral oophorectomy
3. Postmenopausal female
  - A postmenopausal state is defined as no menses for 12 months without an alternative medical cause. A high follicle stimulating hormone (FSH) level in the postmenopausal range may be used to confirm a postmenopausal state in women not using hormonal contraception or hormonal replacement therapy (HRT). However, in the absence of 12 months of amenorrhea, a single FSH measurement is insufficient.
  - Females on HRT and whose menopausal status is in doubt will be required to use one of the non-hormonal highly effective contraception methods if they wish to continue their HRT during the study. Otherwise, they must discontinue HRT to allow confirmation of postmenopausal status before study enrolment.

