## **5.4. Scientific Rationale for Study Design**

This is a drug-drug interaction study in healthy males and females of non-child bearing potential. Participants will be dosed with nemralisib before and during co-administration of itraconazole and will act as their own control. A sufficient wash-out period is included (at least 14-days between nemralisib dose administrations in Period 1 and in Period 2) to remove any effect or residual systemic exposure from the first dose of nemralisib before starting itraconazole dose administration in Period 2.

An open label design was considered appropriate because the primary objective (pharmacokinetic parameters) does not require blinding and no pharmacodynamic markers were included in the study.

Woman of child bearing potential are excluded from participation in this study because itraconazole has shown reproduction toxicity in animal studies. In addition, there is limited information on the use of itraconazole during pregnancy and during post-marketing experience, cases of congenital abnormalities have been reported.

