##### b. Female participants:

A female participant is eligible to participate if she is not pregnant (see [Appendix 5](#)), not breastfeeding, and not a woman of childbearing potential (WOCBP) as defined in [Appendix 5](#).

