#### **Prior/Concomitant Therapy**

6. Past or intended use of over-the-counter or prescription medication including herbal medications within 14 days prior to dosing (Specific medications listed in Section [7.7](#) may be allowed)

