### **9.2.5. Pregnancy**

- Details of all pregnancies in female partners of male participants will be collected after the start of study treatment and until follow-up.
- If a pregnancy is reported, the investigator should inform GSK within 24 hours of learning of the pregnancy and should follow the procedures outlined in [Appendix 5](#).
- Abnormal pregnancy outcomes (eg, spontaneous abortion, fetal death, stillbirth, congenital anomalies, ectopic pregnancy) are considered SAE.

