**Table 4 Protocol-Required Safety Laboratory Assessments**

Laboratory Assessments	Parameters			
Hematology	Platelet Count	RBC Indices: Mean corpuscular volume Mean Corpuscular Hemoglobin %Reticulocytes		White Blood Cell count with Differential: Neutrophils Lymphocytes Monocytes Eosinophils Basophils
	Red Blood Cell (RBC) Count			
	Hemoglobin			
	Hematocrit			
Clinical Chemistry 	Blood Urea Nitrogen (BUN)	Potassium	Aspartate Aminotransferase (AST)/ Serum Glutamic-Oxaloacetic Transaminase (SGOT)	Total and direct bilirubin
	Creatinine	Sodium	Alanine Aminotransferase (ALT)/ Serum Glutamic-Pyruvic Transaminase (SGPT)	Total Protein
	Glucose (fasted at screening only)	Calcium	Alkaline phosphatase	
Routine Urinalysis	
 
• Specific gravity
 
• pH, glucose, protein, blood, ketones, bilirubin, urobilinogen, nitrite, leukocyte esterase by dipstick
 
• Microscopic examination (if blood or protein is abnormal)
 
			
Other Screening Tests	
 
• Follicle-stimulating hormone and estradiol (as needed in women of non-childbearing potential only)
 
• Alcohol breath test and urine drug screen (to include at minimum: amphetamines, barbiturates, cocaine, opiates, cannabinoids and benzodiazepines)
 
• Urine cotinine
 
• Serology (HIV antibody, hepatitis B surface antigen [HBsAg], and
 
			

Laboratory Assessments	Parameters
	hepatitis C virus antibody) The results of each test must be entered into the CRF.

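### Appendix 5 lets a woman on HRT whose menopausal status is in doubt count as not of childbearing potential without confirmation, which conflicts with Section 5.4, and the rest of the protocol does not provide for her

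*Protocol*

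**What the plan says.** Section 5.4 of the protocol gives the rule and its reason: "Woman of child bearing potential are excluded from participation in this study because itraconazole has shown reproduction toxicity in animal studies". It offers no contraception alternative. Inclusion criterion 6b in Section 6.1 requires that a female participant is not pregnant, "not breastfeeding, and not a woman of childbearing potential (WOCBP"), and refers to Appendix 5 on both pregnancy and childbearing potential.

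Appendix 5 opens with a general definition: "A woman is considered fertile following menarche and until becoming post-menopausal unless permanently sterile (see below". It then lists the women who fall outside it: premenarchal, premenopausal with documented surgery, and postmenopausal. The postmenopausal item has two bullets. The first defines the state by 12 months without menses and no other medical cause, and allows a high FSH to confirm it in women who use neither hormonal contraception nor HRT. The second reads "Females on HRT and whose menopausal status is in doubt will be required to use one of the non-hormonal highly effective contraception methods" if they want to stay on HRT while in the study. It continues: "Otherwise, they must discontinue HRT to allow confirmation of postmenopausal status before study enrolment".

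**The concern.** The list in Appendix 5 is there to identify women who cannot become pregnant. A woman whose menopausal status is in doubt has not been shown to belong on it. Contraception lowers her risk of pregnancy but does not settle the doubt. Because criterion 6b takes its definition from the appendix, a site that follows the appendix to the letter can find that she meets 6b.

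Once enrolled, she would receive one inhaled dose of nemiralisib in each period and repeated daily itraconazole in Period 2. The itraconazole exposure is the one that Section 5.4 sets out to keep from women who could conceive. The rest of the protocol reads as if no such woman were in the study, so the site would have little to follow on testing, duration of contraception or follow-up of a pregnancy.

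**Working it through.** No arithmetic applies. The check sets the sections side by side.

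1. **Entry under 6b.** The opening definition in Appendix 5 releases a woman only when she is postmenopausal or permanently sterile. A woman in doubt has established neither. The second bullet nevertheless sits under the heading for women outside the definition and gives two branches. In the first she keeps HRT and uses non-hormonal contraception, and nothing is said about confirming her status. In the second she stops HRT and her status is confirmed before enrolment. Only the second branch removes the doubt. In the first, FSH is not available as confirmation, because the preceding bullet restricts that use to women not on HRT. She formally meets 6b by either branch. The conflict is with Section 5.4 and the opening definition, not with 6b itself.

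2. **Medication rules.** Exclusion 6 bars "Past or intended use of over-the-counter or prescription medication including herbal medications within 14 days prior to dosing", with an exception for medicines covered in Section 7.7. Section 7.7 extends the restriction to the follow-up visit, names paracetamol as permitted, and leaves other medicines to a case-by-case opinion that they will not interfere with the study. Neither section mentions HRT. A woman on the first branch therefore needs this allowance as well. The test applied is interference with the study, not fertility. Appendix 5 speaks of staying on HRT without referring to either section.

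3. **Pregnancy testing.** Tables 1 to 3 of the schedule of activities, repeated in SAP Appendix 1, contain no pregnancy test. Among the screening tests, Table 4 lists "Follicle-stimulating hormone and estradiol (as needed in women of non-childbearing potential only") but no pregnancy test. Criterion 6b sends the reader to Appendix 5 on not being pregnant, and Appendix 5 names no test. Appendix 2 lets the investigator add tests but requires none.

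4. **Contraception period.** Criterion 6a sets a period for men: the treatment period and at least 10 days after the last dose. Criterion 6b sets none for women. The contraception guidance in Appendix 5 has a section for male participants only, and Table 5 does not mark which methods are non-hormonal.

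5. **Pregnancy collection.** Section 9.2.5 states: "Details of all pregnancies in female partners of male participants will be collected after the start of study treatment and until follow-up". The collection procedure in Appendix 5 is likewise written for partners only. Section 9.2.5 also has a sentence, not limited by sex, that the sponsor is informed within 24 hours of a reported pregnancy, and it treats abnormal outcomes as serious adverse events. That sentence refers the site to the Appendix 5 procedures, which do not cover a female participant.

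6. **Number affected.** About 20 participants aged 18 to 75 are planned. The documents give no sex split and no rate of HRT use, so no count can be derived.

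**The case against.** The strongest reply has several parts. The bullet is nested under the postmenopausal item, so it can be read as an added precaution for women already thought to be postmenopausal. Criterion 6b adopts Appendix 5 as its definition, so nothing formally contradicts 6b. The medication rules are a second hurdle. Criterion 6b still requires that she is not pregnant, and the investigator may add a test. All of this is fair, and it makes such an entry unlikely. It does not remove the inconsistency: the bullet is expressly about women whose status is in doubt, and the medication hurdle does not ask about fertility.

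A reader might also infer more than the documents support:

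- **That she enters on contraception alone.** She also needs the allowance under Exclusion 6 and Section 7.7. What is missing is confirmation of her status.
- **That a pregnancy in her would have no reporting route.** The general 24-hour sentence in Section 9.2.5 gives one. The gap is in collection and follow-up.
- **That her status could not be established at all while on HRT.** The restriction applies to FSH. The definition itself rests on 12 months without menses.
- **That, with waivers forbidden in Section 6, she is both eligible and excluded.** Exclusion 6 contains its own exception, and using it is not a waiver.
- **That HRT would disturb the interaction estimate.** The documents do not say that HRT affects CYP3A4 or nemiralisib, and Section 7.7 makes any allowance conditional on non-interference.

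**Conclusion.** The point holds as an internal inconsistency in eligibility. Appendix 5 allows a woman of unresolved fertility to be classed as not of childbearing potential without confirmation before enrolment, against the stated reason for exclusion in Section 5.4 and the appendix's own definition. The protocol then has no scheduled pregnancy test, no contraception period and no pregnancy follow-up procedure for her.

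The size is unknown. That it is small is a judgement, resting on a study of about 20 people and on the second hurdle in the medication rules. The sample size, the analysis populations and the primary pharmacokinetic analysis do not depend on it. It merits correction because the exposure concerned is the one that Section 5.4 is written to prevent and because the wording repair is cheap.

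**What to change.** Reconcile the second bullet of the postmenopausal item in Appendix 5 with that appendix's opening definition, Section 5.4, criterion 6b, Exclusion 6 and Section 7.7, so that one eligibility rule applies to women whose menopausal status is in doubt. State how HRT is treated under the medication rules.

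If the sponsor keeps the contraception route, these places need to be brought into line with it: Section 5.4; the schedule of activities and Table 4, on how not being pregnant is to be established; the contraception period for female participants; and Section 9.2.5 with the pregnancy procedure in Appendix 5, so that they cover a female participant. The schedule copied into SAP Appendix 1 would follow. Which clinical rule applies is for the sponsor to decide.

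If Section 5.4 stands as written, the cost is limited to wording in the eligibility sections, with no added visit or sample, and possibly a few women screened out. If the route is kept, several sections change, together with any procedure the sponsor chooses to add.
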